## Study Activities

1. \* Select which study type best describes the majority of the study. Your response will help determine which IRB panel should review this.

- Bio-Medical
- Qualitative - Social/Behavioral/Education (SBE)
- Quantitative - SBE
- Mixed Method - SBE
- Mixed Method - Biomedical

2. \* This study will involve (check all that apply)

- procedures such as surveys, interviews, field studies, focus groups, educational tests, deception, psycho-physiological testing, any other similar data collection
- secondary data analysis procedures such as analysis of information collected for non-research purposes (includes both retrospective and prospectively collected information), or analysis of data previously collected for a prior research study
- drugs, devices, experimental interventions, biohazards, radiation, other medical or surgical procedures

ID: HM20011025

View: SF - Bio-Med Project Details

## Bio-Med Project Details

1. \* Select all details that apply

---

Drugs, Biologics, Supplements, and/or Other Compounds

---

**Placebo**

---

Washout Period

---

**Device Evaluation**

---

Bio-Hazards, Other Toxins, Recombinant DNA/Gene Transfer

---

Radiation Exposure and/or Scans involving radiation (PET, MRA)

---

Stem Cells

---

Expanded Access - Treatment Use of an Investigational Product

---

**Other Medical or Surgical Procedures**

---

**Protected Health Information (PHI)**

---

ID: HM20011025

View: SF - Bio-Med Placebo/No Treatment

## Bio-Medical Placebo/No Treatment

**1. \* Describe and justify the use of placebo**

Applying primer on a surface of a tooth is a necessary step to achieve optimal bonding of orthodontic brackets. Typical primers used in the clinical practice do not contain fluoride. This study evaluates the effects of a newly introduced fluoride releasing primer (OpalSeal), against a conventional, non-fluoride containing primer (Transbond XT). Since Transbond XT does not contain fluoride, it can be considered a placebo. Opal Seal and Transbond XT are identical in their color, consistency and application. This ability to blind the participants as well as random assignments will allow us to estimate the true effects of OpalSeal.

ID: HM20011025

View: SF - Bio-Med Device Evaluation Details

## Bio-Medical Device Evaluation Details

**1. \* Select the type of device evaluation this study will involve**

---

**Marketed Medical Device (including 510k device)**

---

Marketed but new indication or intended use

---

Mobile application with regulatory discretion

---

Mobile application without regulatory discretion

---

Investigational device

---

**2. \* List devices this study will involve**

| Device   | Manufacturer      | IDE        | IDE Holder   | Doc |
|----------|-------------------|------------|--------------|-----|
| OpalSeal | Opal Orthodontics | IDE Exempt | Not Required |     |

**3. \* For each device listed above upload documentation of the approved use(s) (operation manual, instructions for use, etc.) or a detailed description of the design, use, and risks of the device**

- If 'Investigational Medical Device' or 'New Use for Marketed Medical Device' was selected above AND the device qualifies for IDE exemption under under 21 CFR 812.2(c), upload one of the following documents for each applicable device
  - A document explaining how the device's use in this study meets one of the categories for IND exemption under 21 CFR 812.2(c)
  - External sponsor's protocol including IDE exemption information
  - Communication from the external sponsor verifying the IDE exemption
  - Communication from the FDA with verification of IDE exemption

ID: HM20011025

View: SF - Social/Behavioral Project Details

## Social/Behavioral Project Details

**1. \* Select all that apply to this study**

---

Analysis of Information Originally Collected for Non-Research Purposes

---

Analysis of Data Originally Collected for a Previous Research Study

---

Behavioral Intervention or Experimentation

---

Observations

---

Educational Settings/Assessments/Procedures

---

Population Based Field Study

---

- Psychophysiological Testing
- Deception
- Oral History
- Interview/Focus Groups
- Surveys/Questionnaires/Psychometric Testing
- None of the Above

2. \* Will any portion of the research be potentially upsetting to the participants

- Yes
- No

3. If Yes, describe the nature of the questions and how you will manage the situation should participants become upset

4. Upload ALL instruments/guides that will be used, including scripts/questions to guide interviews, surveys, questionnaires, observational guides, etc.

ID: HM20011025

View: SF - Data Collection Details

## Data Collection Details

1. \* Select all involved in the study

- Specimen/Biologic Sample Collection
- Protected Health Information (PHI)
- Secondary Data or Specimens Not From a Registry or Repository
- Audio/Video
- Use of Internet for Data Collection
- Registries/Repositories (Includes Accessing, Contributing or Creating)
- None of the Above

2. \* Select all identifiers that will be collected as part of this study (including for recruitment, data gathering, data analysis, etc.), even if the data will eventually be anonymized

- Names
- Geographic Locators Below State Level
- Social Security Numbers
- Dates (year alone is not an identifier)
- Ages >89
- Phone Numbers
- Facsimile Numbers
- E-mail Addresses
- Medical Record Numbers
- Device Identifiers
- Biometric Identifiers
- Web URLs
- P Addresses
- Account Numbers
- Health Plan Numbers
- Full Face Photos or Comparable Images
- License/Certification Numbers
- Vehicle ID Numbers
- Other Unique Identifier
- No Identifiers
- Employee V#

3. If "Other Unique Identifier" was selected above, describe the identifiers

4. \* Will participants be able to withdraw their data (paper, electronic, or specimens) from the study if they no longer wish to participate

- Yes  
 No

5. If yes above, describe how participants will be able to withdraw their data

ID: HM20011025

View: SF - Sample Collection

## Sample Collection

1. \* Select all of the types of samples that will be collected as part of this study

- Amniotic Fluid
- Blood
- Buccal Smears
- Saliva
- Tissue
- Urine
- Other
- None of the Above

2. If Other, please describe the type of sample being collected

1. Teeth extracted at the time of extraction

3. \* Describe how the samples will be collected and the collection schedule. For each type of sample, include information about

- The procedures that will be followed to collect the sample
- The role(s) of the individuals who will collect the sample
- The volume/size range of the sample
- The timing and frequency of sample collection

Conventional Clinical Protocol:

Patients who require extractions will be referred to an oral surgeon (of their choice) for extraction of teeth. Patients will report to the clinic with the dates of scheduled extractions (with dentists' name and contact information) and they will be seen in the clinic for removal of wires and brackets (from the two teeth that would be extracted). The surgeon cannot remove teeth if the brackets and wires are still in place.

Within a few days after extractions, the patients will report to the clinic for putting the wires back. This way there is minimal disruption to the orthodontic treatment.

For study participants:

When these patients report to the clinic for removal of wires, they will be handed 2 screw-capped plastic jars containing water, clearly labeled right or left for collecting right or left sided teeth. In addition, these jars will also have the initially-assigned, study code, so that the dentist and the patient are blinded to which tooth had OpalSeal. This will not have any PHI that will identify the tooth to the patient by any non-study personnel. The patients will be instructed to hand over the jars to the office staff at the time of extraction. At the end of extraction appointment, the patient will collect the jars (with teeth) and take it home. They will hand over the jars containing the teeth when they return to the clinic to put the wires back on.

The PI can and will independently verify which tooth had OpalSeal when the samples arrive at the laboratory. This additional step will ensure the collected data is robust and valid.

4. \* Will Genetic Testing be conducted on any of the samples

- Yes  
 No

5. \* Will any of the samples be used for a pregnancy test

- Yes  
 No

6. If yes, describe how positive pregnancy results will be communicated to the participant, particularly if minors are involved

7. \* Will any of the samples be used to screen or document alcohol or illicit drug use

- Yes  
 No

8. \* I am aware that I may need to establish a research account with VCUHS Department of Pathology for specimen processing

- Yes  
 No

ID: HM20011025

View: SF - H PAA

## HIPAA

1. \* Describe the protected health information that will be obtained or used in this research

The information that we would collect would include routine patient diagnostic records including radiographs, intraoral photographs as well as treatment plan

2. \* Describe the source(s) of the protected health information

We will use patient electronic health records (axiUm and Dolphin) to identify potential study participants. Access to these databases is protected by a secure username and password.

3. \* Explain how the PHI collected or used in this research is the minimum necessary to accomplish this research

There is no way to prospectively to identify eligible subjects without accessing their medical records. The PHI requested is minimum necessary to identify and recruit potential study participants.

4. \* Select all pathways this research will employ to use or access PHI

De-Identified Data (none of the 18 identifiers are recorded or associated with the research data)

Limited Data Set

Waiver of Authorization

Partial Waiver of Authorization

Signed Authorization Combined with Consent Form

Signed Authorization as Stand-Alone Form

ID: HM20011025

View: SF - Partial Waiver of Authorization

## Partial Waiver of Authorization

### 1. \* Select the purpose for requesting the partial waiver of authorization

Identify possible participants to recruit for the study

Waive some elements of authorization (such as signature)

### 2. If you selected "Waive some elements of authorization" above, list the elements you want to waive and explain why

We will use Partial Waiver of Authorization to access patients' electronic records and identify potential study participants.

### 3. \* Explain how the partial waiver of authorization poses no greater than minimal risk to participants' privacy

All protections of H PAA associated with patient care will also apply for study participants.  
Therefore this use of PHI is minimal risk

### 4. If you selected "Identify possible participants to recruit" above, describe when will the identifiers be destroyed for those who do not eventually enroll in the study?

Following Participant Contact

Following Participant Enrollment

Upon Reaching Study Accrual Objectives

Other

### 5. \* Other than the PI and research personnel identified in this research application, who else will have access to the Protected Health Information?

The study team will have the sole access to the PHI

### 6. \* Explain why the study cannot practicably be conducted without the partial waiver of authorization

We need access to patients' dental records to be able to screen and identify potential study participants.

### 7. \* In applying for a partial waiver of authorization, the PI agrees to the following

- the identifiers used for this research study will not be used for any other purpose or disclosed to any other person or entity (aside from members of the research team identified in this application), except as required by law
- if at any time the PI wants to reuse this information for other purposes or disclose the information to other individuals, the PI will seek approval from the IRB/Privacy Board
- the PI will comply with VCU HIPAA policies and procedures and to the use and disclosure restrictions described above
- the PI assumes responsibility for all uses and disclosures of the PHI by members of the study team

Yes

No

ID: HM20011025

View: SF - Existing Data/Specimen Details

## Existing Data/Specimen Details

### 1. \* Describe the source and nature of the data/specimens being obtained

The premolar teeth will be extracted from the participants during the appropriate treatment time. It is important to note that the inclusion criteria for participating in this study includes the need for premolar extractions as per the patient elected treatment plan.

### 2. \* Describe how you have access to the data/specimens

The patient will bring in the extracted teeth in the specified containers (with no PHI) and hand them over to the Orthodontic Clinic at the follow up appointment to place the archwires back.

### 3. \*

Describe any identifiers or coded information that will be obtained that can be linked directly or indirectly to the identity of participants

Patients will have a numerical code assigned to them (with no PHI). Extracted teeth will be placed in jars (marked Right or Left) by the staff in the Oral Surgery Clinic and handed over to the patient who will then return these to the Orthodontic clinic. The resident will place the teeth in different jars (labeled with original study code). The key will be available to the study team.

### 4. \* Did individuals provide consent for research when the data / samples were originally collected?

Yes

No

### 5. If yes, did the consent allow for sharing of the data

Yes

No

## Data Confidentiality and Storage

Confidentiality refers to the way private, identifiable information about a participant or defined community is maintained and shared.

1. \* Specify where this study's paper and electronic research data and/or physical specimens will be stored and how they will be secured from improper use and disclosure

**See the help text for additional guidance.**

All signed informed consent documents and completed surveys will be stored in a locked cabinet in the PI's office. The extracted teeth will be collected in jars containing no PHI from the oral surgery clinic and will be stored in a refrigerator in locked laboratory (Dental Materials Laboratory, Wood Building 101) until analysis.

In our study, every patient will serve as his/her own control. This is because every patient will have two teeth extracted, one of which will receive OpalSeal and the other, Transbond XT. We will use a computer generated random number table to determine which tooth will receive OpalSeal or Transbond XT. We will generate a code based on:

- order of patient enrollment and
- whether the tooth received OpalSeal (e) or Transbond XT (c)
- date of tooth extraction

2. This key that links code to the patient will be stored in the PI's office computer that has restricted access (only to study personnel).

3. The key will be destroyed when the extracted teeth are collected from the patient. Since we would not be needing any PHI, this would decrease the risk of loss of confidentiality.

2. \* Who will have access to study data

PI, co-investigator, student researcher, and statistician will have access to the study data. They are all part of the study team.

3. \* If the study will code (i.e. de-identify) the research data by replacing subjects' names with assigned subject IDs, explain the following aspects of the coding process

1. The process for how subject IDs will be generated/assigned (e.g. random, sequential)

2. Whether there will be a key that links the subject ID with direct identifiers.

If a key will be created, describe

3. The place where the key will be stored

4. The role(s) of all individuals who will have access to the key

5. When the key will be destroyed

**See the help text for additional guidance.**

The statistician will provide the study team with the computer generated random table. The study participants will be sequentially assigned a 3-digit code followed by R or L (for Right or Left) for OpalSeal. For example, patient 1 may be 001R. The key to the code will be kept by the PI in a password-protected computer and will be destroyed at the end of study.

We will have 2 codes to simplify the process and decrease confusion:

The jars handed over to the patients will have fields for date; patient initials; tooth number; Right or Left sides. Patient will be given these jars and will be instructed to hand this over to the staff at the oral surgery clinic who will place the extracted teeth in the correct containers.

Once the patient hands over the containers (with extracted teeth) to the Orthodontic Clinic, the teeth will be transferred to another jar with the original study codes. The resident and or members of the study team will collect the jars containing the teeth directly from the participant.

4. \* Will the sponsor or investigator obtain a certificate of confidentiality for this study

- No - CoC will not be Obtained
- Yes - CoC has been Obtained
- Yes - CoC Request is Pending
- Yes - Plan to Submit CoC Request

5. If the Certificate of Confidentiality has been obtained by the PI, upload it here

6. \* What will happen to the research records when the research has been completed

- Stored indefinitely with identifiers removed
- Stored indefinitely with identifiers attached
- Destroyed at the end of study once the minimum time required for data retention has been met per VCU Data Retention Policy and/or sponsor retention requirements
- Destroyed when notified by sponsor but not less than the minimum time required for data retention per VCU Data Retention Policy
- Other

7. If Other, explain

8. If "stored indefinitely with identifiers attached", explain why identifiers are necessary

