All specimens will be transferred into 0.1% thymol solution (disinfectant) and stored until analysis. There will be no personally identifiable information on the jars. Samples will undergo the following tests:

- a. Scanning electron microscopy to analyze the surface topography
- b. Micro-CT to quantify the mineral density
- c. Atomic force microscopy to test surface roughness and hardness
- d. Fluorescence to quantify the residual amount of OpalSeal

The survey will help us understand how the patient controlled factors affect the incidence of WSL. For example, are right-handed patients more likely to develop WSL on the right side?

"The statistician will generate and provide a computer generated random assignment table to the resident [REDACTED]. The resident will be the only person that will be providing the interventions (OpalSeal or TransbondXT) to the study participants."

1. Bonding brackets on to-be-extracted teeth: Placing brackets on teeth are fundamental to moving teeth and teeth will have a bracket attached at the start of treatment. However, teeth planned for extractions do not receive any brackets in routine clinical practice. In our study though, we will place brackets even on to-be-extracted teeth until they are extracted. Since every patient will have at least two teeth that would be extracted, one of them would receive OpalSeal while the other will receive Transbond XT. The procedures for bonding will be consistent with clinical procedures and protocol for any orthodontic patient treated in the clinic.
2. Administering OpalSeal: OpalSeal will be applied to the teeth of interest following manufacturer's instructions for use (refer to the attached document).

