## VCU Site Details

1. \* Select all VCU sites that will be utilized in this study

---

 Children's Hospital of Richmond at VCU

---

 Clinical Research Services Unit (CRSU)

---

 Massey Cancer Center

---

 VCU Health Community Memorial Hospital

---

 VCU Medical Center downtown

---

 VCU Monroe Park Campus

---

 VCU Qatar

---

 Other VCU Site

2. \* Provide details regarding each VCU Site including

- what clinics / facilities will be used

- resources that are available for the conduct of this study

Informed consent and collection of samples (extracted teeth) will occur at the Orthodontic Clinic at VCU School of Dentistry on the MCV campus.

Once the patient hands over the samples, water will be replaced with 0.1% Thymol solution (disinfectant). Samples in disinfectant will be stored in [name] laboratory in the School of Dentistry in a refrigerator until ready for analysis. The samples will be subject to micro CT, AFM at core facilities in the School of Engineering. These samples will not have any personal identifiers and people working with these samples will not know the source (patient information).

ID: HM20011025

View: SF - Study Funding

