## Privacy

1. \* Privacy is an individual's right to control how others view, record, or obtain information about them. When privacy is violated it can involve such things as being asked personal questions in a public setting being publicly identified as having a particular characteristic or diagnosis being photographed, videotaped or observed without consent or disclosing personal information.

- Describe how participants' privacy will be protected during
- identification,
  - recruitment,
  - screening,
  - the consent process,

- conduct of the study, and
- data dissemination

The screening, recruitment and consent procedures will be carried out in a private room located within the orthodontic clinic ensuring complete privacy.

All study related information about the participant will be stored in a secure server in the PI's computer and will not be accessible to anyone other than study personnel. The samples (jars with extracted teeth) will be coded to ensure patient privacy. No personally identifiable information will be attached to the specimens so that no one working in the laboratory will know the source.

Any publications that can arise from this study will protect patient privacy by not disclosing any identifiable information. Signed informed consent documents will be stored in a locked cabinet in the PI's office.

ID: HM20011025

View: SF - Costs to Participants

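### Both spelled-out forms of the study code contain the allocation, and the original study code labels the jars from which the teeth go to laboratory testing

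*Protocol*

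**What the plan says.** **How the code is built.** Data Confidentiality and Storage, item 1, makes it from order of enrolment, the date of extraction, and "whether the tooth received OpalSeal (e) or Transbond XT (c"). Item 3 of the same section defines it differently: "The study participants will be sequentially assigned a 3-digit code followed by R or L (for Right or Left) for OpalSeal", with 001R as the example for patient 1. Existing Data/Specimen Details, item 3, mentions a numerical code for each patient and says nothing more about its content.

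**Where the code is put.** Existing Data/Specimen Details, item 3: "The resident will place the teeth in different jars (labeled with original study code"). Data Confidentiality and Storage, item 3, agrees that "the teeth will be transferred to another jar with the original study codes". Neither place says which definition is meant.

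**What laboratory workers are not told.** VCU Site Details, item 2, says that "people working with these samples will not know the source (patient information"). Privacy, item 1, says that specimens carry no personal identifiers, "so that no one working in the laboratory will know the source".

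**The jars the patient carries.** Sample Collection, item 3, marks them right or left, adds the study code, and credits that code with keeping dentist and patient blinded to which tooth had OpalSeal. Data Confidentiality and Storage, item 3, announces two codes and lists the fields on these jars as date, initials, tooth number and side, with no study code.

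**The concern.** In a split-mouth trial the arm of one tooth fixes the arm of the other, so a label that gives away one tooth gives away the pair. A reader who can tell the arm and expects a benefit may score the OpalSeal tooth more kindly. Pairing does not cancel this, because the error falls on the within-patient difference, which is the quantity being estimated.

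The readings at risk are those that need judgement. One is surface topography by scanning electron microscopy. The other is the white spot lesion score on which the sample size is based (Study Population, item 3), if that score is read from the coded teeth, which the protocol does not say. Once teeth have been read under a revealing label, no later analysis can restore the masking.

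**Working it through.** No power or sample-size formula applies. The check sets the statements side by side and counts labels.

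**1. What each form of the code reveals**

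| Form | Where (Protocol) | Unit | What the label shows |
|---|---|---|---|
| Order, e/c letter, extraction date | Data Confidentiality and Storage, item 1 | Tooth | The arm, directly |
| Number plus OpalSeal side (001R) | Data Confidentiality and Storage, item 3 | Patient | The arm, if the reader knows the rule and the tooth's side |
| Numerical code, undefined | Existing Data/Specimen Details, item 3 | Patient | Cannot be determined |

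**2. Number of labels.** Planned recruitment is 35 and the sample-size calculation uses 30. With two study teeth per patient:
- 35 × 2 = 70 teeth; 30 × 2 = 60 teeth.
- e/c form: 70 of 70 labels would state the arm (60 of 60 at the smaller number).
- R/L form: 35 codes over 70 jars, so 70 / 35 = 2 jars share each code.

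**3. The R/L form worked through for code 001R**
- Right tooth: side equals suffix, so OpalSeal.
- Left tooth: side differs from suffix, so Transbond XT.
- Side unknown: both jars read 001R, and the two teeth cannot be told apart.

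So this form has a defect either way. Without a side mark it cannot identify the tooth, which a paired analysis needs. With a side mark, anyone who knows the rule can read the arm. The protocol does not say whether the final jars carry a side mark.

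**4. Does the key protect the arm?** Item 1 says: "This key that links code to the patient will be stored in the PI's office computer". That key guards identity. In both spelled-out forms the arm sits in the code itself and can be read without the key.

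**5. The patient-held jars.** Under Sample Collection, item 3, side mark and study code stand on the same jar. With the R/L form, those are the two pieces needed to work out the arm; only ignorance of the rule hides it. A code that contains the allocation cannot itself supply the blinding credited to it.

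**6. Which tests are exposed.** Research Description, item 4, lists four:
- micro-CT, to quantify mineral density;
- atomic force microscopy, to test roughness and hardness;
- fluorescence, to quantify residual OpalSeal;
- scanning electron microscopy, to analyse surface topography.

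The first three are described as measurements and are less exposed. Microscopy of topography is the one not described as a quantified reading.

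**The case against.** The strongest reply is that a revealing label is possible but not established.

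- The numerical code in Existing Data/Specimen Details appears in the same answer as the original study code, and a bare number would carry no allocation.
- The e/c form includes the extraction date. Research Description, item 4, puts extraction about three months away, so that form could not be complete at enrolment and fits the words original or initially assigned poorly.
- The R/L form needs both the rule and the side, and nothing says that core-facility staff know either.
- The statements in VCU Site Details and Privacy answer confidentiality questions; they were not written as a masking rule.
- Residual primer may disclose the arm whatever the label says.

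Most of this stands, and it limits the point. It does not remove it. The number is never defined as free of allocation, both definitions that are given contain it, and the extraction date is known by the time of re-jarring, so the e/c form cannot be excluded there.

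A reader might infer more than the documents support:

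- *That all specimen labels will state the arm, or that laboratory staff are unblinded.* The first is true only of the e/c form. No text says who reads the teeth or what they are told about the code.
- *That participant blinding is lost.* Research Description, item 4, has the jars handed over typically a day or two before extraction, after nearly all of the exposure, and nobody is said to explain the suffix to patients. Little bias can arise there; what remains is a conflict of wording.
- *That the random table is handled inconsistently.* Research Description says "The statistician will generate and provide a computer generated random assignment table to the resident", while Data Confidentiality and Storage gives it to the study team. The two are compatible: the first does not say that the resident alone holds it.

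**Conclusion.** The point holds in a limited form. As written, the protocol allows the arm, or half of what is needed to work it out, to stand on the label of every tooth sent for testing. It gives three descriptions of the code without saying which one applies, and no statement masks the readers to arm. The finding rests on what the label is said to contain, not on that silence alone.

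The effect on the treatment estimate is unknown. Exposure is confined to judged readings: topography for certain if it is scored by eye, and the white spot lesion score only if it is read from the coded teeth. The count of 70 labels assumes 35 patients with two study teeth each, and its direct form assumes the e/c code. The conflict over the patient-held jars is real but minor. This should be fixed before teeth are re-jarred, and my confidence in the bias concern is moderate.

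**What to change.** 1. **Label.** At the re-jarring already planned, give each tooth a random specimen number from a list prepared by the statistician, with no arm letter and no side.
2. **Custody.** The statistician keeps the link from specimen number to patient, side and arm, and withholds it from readers until all readings are locked. The principal investigator's check of which tooth had OpalSeal, made when samples arrive (Sample Collection, item 3), can stay where it is, provided that its result is not shared with readers before the lock.
3. **One definition.** Use a single description of the study code in Sample Collection item 3, Existing Data/Specimen Details item 3, and Data Confidentiality and Storage items 1 and 3. State whether the patient-held jars carry a code, and do not credit a code that contains the allocation with blinding anyone.

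Optionally, run the fluorescence test for residual OpalSeal after the other readings, since its result may itself suggest the arm.

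The cost is some wording, one extra number list and different labels. The downside is an added transcription step: the list becomes the only link between tooth and arm, so a second person should check each entry. No visit, procedure or sample size changes.
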